# 15. PERFORMANCE QUALIFICATION OF SAS® PROGRAMS

The analysis and summary of data from this study will be performed using SAS® 9.4 (or a later release if available). All SAS® programs used in the production of statistical analyses, tables, listings, and figures described in this SAP will undergo performance qualification (verification that the program produces the intended output) in accordance with department standard operating procedures. The performance qualification may include independent programming and/or peer review of the SAS® log files. In addition, tables, figures, listings, and statistical analysis output will be independently reviewed for completeness and accuracy.

## **17. APPENDICES**

#### 17.1. Implementation of Multiple Imputation for the Primary Endpoint and First Key Secondary Endpoint

For the primary and first key secondary endpoint that require multiple imputation, the following steps will be taken.

1) For subjects on study drug and are missing the endpoint at the timepoint of interest, impute missing data using a regression-based multiple imputation model based on data from subjects with non-missing endpoint data at the timepoint of interest within the same treatment group. The model will include the baseline value for the endpoint, sex, and pubertal stage.

2) For subjects in the crinecerfont treatment group off study drug prior to timepoint of interest and are missing the endpoint at the timepoint of interest, impute missing data using a regressionbased imputation model based on data from Retrieved Dropouts. If there are an insufficient number of Retrieved Dropouts, the endpoint will be imputed from subjects in the placebo treatment group. For similar subjects in the placebo treatment group, missing data will be imputed using non-missing data from subjects in the placebo treatment group. The model will include the baseline value for the endpoint, sex, and pubertal stage.

Note that for the regression-based multiple imputation models described above, the values recorded on the eCRF will be used instead of those recorded at the time of randomization in the IRT.

The number of imputed datasets created from the steps above for each endpoint is 100. After the multiply-imputed datasets have been created, each of the datasets will be analyzed using the ANCOVA model described in Section 9.2.1. The results of these analyses will be combined using PROC MIANALYZE.

#### 17.2. Implementation of Multiple Imputation for Second Key Secondary Endpoint

The second key secondary endpoint requires the availability of both the glucocorticoid dose at Week 28 as well as androstenedione values used in the assessment of androstenedione control (as defined in Section 6.3.5). For subjects with incomplete or missing data at Week 28 (ie, missing glucocorticoid dose, androstenedione, or both), the following methods will be used to multiply impute the missing data for use in the analysis of the endpoint. The methods of handling each case of missing data are described in text below.

Subjects with a missing glucocorticoid dose, androstenedione, or both at Week 28 will have their data multiply imputed using the fully conditional specifications (FCS) method. This method will be implemented in SAS® 9.4 PROC MI using a series of conditional models (one for each incomplete variable at Week 28). First, the missing Week 28 pre-GC dose androstenedione values will be imputed using a regression-based multiple imputation model and the model will include baseline androstenedione (pre-GC dose), age, and sex (as specified in the eCRF). The subsequent FCS regression model will impute Week 28 glucocorticoid total daily doses (in mg/m^2/day) and the model will include baseline glucocorticoid dose (mg/m^2/day), baseline androstenedione (pre-GC dose), Week 28 androstenedione (pre-GC dose), and sex (as specified

in the eCRF). Note that a minimum of 0 is set for imputed Week 28 pre-GC dose androstenedione values and the Week 28 glucocorticoid daily dose (mg/m^2/day) as it is biologically implausible for either of these values to be less than 0. A random-number generator seed value of 1234 will be used. For subjects missing androstenedione at Week 28, androstenedione "control" will be determined based on the imputed Week 28 androstenedione value and the percent change from baseline to Week 28 in glucocorticoid total daily dose will be set to 0 if the imputed androstenedione value does not indicate "control." The number of imputed datasets created from the steps above is 100.

The above multiple imputation procedure will be conducted in more than one PROC MI step so that subjects with missing data are correctly imputed from subjects with complete data based on the rules defined below:

- For subjects who are on study drug at Week 28 and are missing one or both components of the primary endpoint, their missing Week 28 data will be imputed from subjects within the same treatment group with non-missing data at Week 28 (Week 28 Completers).
- For subjects who are off study drug at Week 28 and are missing one or both components of the primary endpoint, their missing Week 28 data will be imputed from subjects who are classified as Retrieved Dropouts (Section 6.4). If there are an insufficient number of Retrieved Dropouts, the missing endpoint values will be imputed from subjects in the placebo treatment group. For subjects in the placebo treatment group, missing data will be imputed using non-missing data from subjects in the placebo treatment group.

The multiply-imputed datasets generated from the steps above will be set back together prior to the final analysis steps.

After the multiply-imputed datasets have been created, each of the 100 datasets will be analyzed using the ANCOVA model described in Section 9.2.1. The results of these analyses will be combined using PROC MIANALYZE.

## 17.3. Implementation of Tipping Point Analysis for the Primary Endpoint

A tipping point sensitivity analysis will be performed to assess the robustness of the missing data assumptions for the primary endpoint. The following steps will be taken to implement the tipping point analysis:

- 1) For the 100 imputed datasets created (as described in Section 17.1), if a subject was originally missing a Week 4 androstenedione value, add *delta* (see rules below) to the imputed Week 4 androstenedione value. Calculate the change from baseline to Week 4 in androstenedione for all subjects:
  - If Week 4 androstenedione is non-missing: change from baseline = Week 4 androstenedione value baseline androstenedione value;
  - If Week 4 androstenedione is missing and the subject is in either the crinecerfont treatment group or placebo treatment group: change from baseline = Week 4 delta-adjusted imputed androstenedione value baseline androstenedione value.
- 2) Analyze the change from baseline to Week 4 in androstenedione in each of the 100 imputed datasets using ANCOVA (as specified Section 9.2.1) using PROC MIXED. Use

PROC MIANALYZE to combine the results and obtain the LS mean statistics (within treatment, and treatment differences).

3) If the p-value in the previous step was not significant (ie, >0.05), then no additional analyses are needed. If the p-value was significant, repeat the previous steps using the next values of *delta*. Continue to do this until significance is lost, or all combinations of deltas (defined for each treatment group) have been analyzed.

The following rules will be used for defining *delta*:

- The initial delta will be = 0 (ie, an analysis of the original, multiply imputed datasets)
- For subjects in the crinecerfont treatment group, the second delta will be = 0.1745 nmol/L. If this is significant, continue to increase delta by 0.1745 until significance is lost.
- For subjects in the placebo treatment group, the second delta will be = -0.1745 nmol/L. Delta will be decreased by 0.1745 until significance is lost.

Delta may be adjusted to approach insignificance faster due to the wide range of values.

# 17.4. Implementation of Tipping Point Analysis for the First Key Secondary Endpoint

A tipping point sensitivity analysis will be performed to assess the robustness of the missing data assumptions for the first key secondary endpoint. The following steps will be taken to implement the tipping point analysis:

- 1) For the 100 imputed datasets created (as described in Section 17.1), if a subject was originally missing a Week 4 17-OHP value, add *delta* (see rules below) to the imputed Week 4 17-OHP value. Calculate the change from baseline to Week 4 in 17-OHP for all subjects:
  - If Week 4 17-OHP is non-missing: change from baseline = Week 4 17-OHP value baseline 17-OHP value;
  - If Week 4 17-OHP is missing and the subject is in either the crinecerfont treatment group or placebo treatment group: change from baseline = Week 4 delta-adjusted imputed 17-OHP value baseline 17-OHP value.
- 2) Analyze the change from baseline to Week 4 in 17-OHP in each of the 100 imputed datasets using ANCOVA (as specified Section 9.2.1) using PROC MIXED. Use PROC MIANALYZE to combine the results and obtain the LS mean statistics (within treatment, and treatment differences).
- 3) If the p-value in the previous step was not significant (ie, >0.05), then no additional analyses are needed. If the p-value was significant, repeat the previous steps using the next values of *delta*. Continue to do this until significance is lost, or all combinations of deltas (defined for each treatment group) have been analyzed.

The following rules will be used for defining *delta*:

• The initial delta will be = 0 (ie, an analysis of the original, multiply imputed datasets)

- For subjects in the crinecerfont treatment group, the second delta will be = 15.15 nmol/L. If this is significant, continue to increase delta by 15.15 until significance is lost.
- For subjects in the placebo treatment group, the second delta will be = -15.15 nmol/L. Delta will be decreased by 15.15 until significance is lost.

Delta may be adjusted to approach insignificance faster due to the wide range of values.

# 17.5. Implementation of Tipping Point Analysis for the Second Key Secondary Endpoint

A tipping point sensitivity analysis will be performed to assess the robustness of the missing data assumptions for the second key secondary endpoint. The following steps will be taken to implement the tipping point analysis:

- For the 100 imputed datasets created (as described in Section 17.2), if a subject was
  originally missing the Week 28 glucocorticoid daily dose value (mg/m^2/day), add *delta*(see rules below) to the imputed Week 28 glucocorticoid daily dose value. Calculate the
  percent change from baseline to Week 28 in the glucocorticoid daily dose for all subjects:
  - If Week 28 glucocorticoid daily dose is non-missing: percent change from baseline = (Week 28 glucocorticoid daily dose value baseline glucocorticoid daily dose value) / baseline glucocorticoid daily dose value x 100;
  - If Week 28 glucocorticoid daily dose is missing and the subject is in either the crinecerfont treatment group or placebo treatment group: percent change from baseline = (Week 28 delta-adjusted imputed glucocorticoid daily dose value baseline glucocorticoid daily dose value) / baseline glucocorticoid daily dose value x 100.
- 2) If the subject does not have androstenedione control at Week 28 (as defined in the second key secondary endpoint) then the percent change from baseline will be set to 0 prior to the analysis of the delta-adjusted imputed datasets.
- 3) Analyze the percent change from baseline to Week 28 in glucocorticoid daily dose in each of the 100 imputed datasets using ANCOVA (as specified Section 9.2.1) using PROC MIXED. Use PROC MIANALYZE to combine the results and obtain the LS mean statistics (within treatment, and treatment differences).
- 4) If the p-value in the previous step was not significant (ie, >0.05), then no additional analyses are needed. If the p-value was significant, repeat the previous steps using the next values of *delta*. Continue to do this until significance is lost, or all combinations of deltas (defined for each treatment group) have been analyzed.

The following rules will be used for defining *delta*:

- The initial delta will be = 0 (ie, an analysis of the original, multiply imputed datasets)
- For subjects in the crinecerfont treatment group, the second delta will be = 1. If this is significant, continue to increase delta by 1 until significance is lost.
- For subjects in the placebo treatment group, the second delta will be = -1. Delta will be decreased by 1 until significance is lost.

Delta may be adjusted to approach insignificance faster due to the wide range of values.

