The second key secondary endpoint of percent change from baseline in glucocorticoid daily dose at Week 28 is based on the glucocorticoid concomitant medications eCRF. The method of collecting concomitant medication data involves entering a start date and stop date for each medication, unless it is ongoing, in which case the "Ongoing?" field is marked as "yes." This differs from assessments that are collected discretely at visits. Additionally, the androstenedione values collected at the Week 28 visit are a critical component to the assessment of this endpoint as subjects who do not maintain androstenedione control and have a decrease from baseline in glucocorticoid total daily dose will have their percent change from baseline value in glucocorticoid total daily dose set to 0. For the purposes of determining the glucocorticoid total daily dose from the eCRF at Week 28, the Week 28 visit date at which the androstenedione values were collected (based on the analysis visit mapping described below) will be used to determine the glucocorticoid dose (as of the same date) to be used for the second key secondary endpoint. If a subject has a Week 28 visit performed based on the analysis visit window but androstenedione was not collected at this visit (ie, missed hormone labs), then the analysis visit date from the collection of the safety labs will be used instead for determining the Week 28 glucocorticoid total daily dose. If both hormone and safety labs were missed at the visit, then the vital signs assessment and its respective Week 28 analysis visit date will be used for determining the glucocorticoid total daily dose. The same methodology described above will be used to determine the glucocorticoid total daily dose from the eCRF at each of the other intermediate visits.

Table 4 includes the analysis visit windows for all assessments, with the exception of those assessments that have a broader window due to more infrequent assessments (ie, every 6-7 months). These more-infrequent assessments include measurements of bone age (via x-ray) and TARTs (via testicular ultrasound). These assessments will use the analysis visit windows defined in Table 6. Table 5 includes the analysis visit windows for subjects who discontinue from study drug prior to OL period or OLE and therefore do not have a first dose date in the OL period or OLE.

Scheduled Visit	Target Study Day	Analysis Window (Study Day Range)
Week 4	28	2 to 43
Week 8	56	44 to 70
Week 12	84	71 to 98

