#### 9.4.2.1. Sensitivity Analyses

The assumptions relative to the ANCOVA model (eg, linearity, normality) for the second key secondary endpoint will be checked and any violations of these assumptions will be handled through non-parametric statistical methods.

A tipping point sensitivity analysis will be performed to assess the robustness of the missingness assumptions. This sensitivity analysis is based on "delta adjustments" which is a commonly used approach to assess the impact of missing data in clinical trials (O'Kelly and Ratitch, 2014). The imputed Week 28 serum glucocorticoid daily dose values (from the MI procedure described in Section 17.2) for subjects in both the crinecerfont treatment group and the placebo treatment group will be delta-adjusted (with a range of plausible penalties for each treatment group) until the treatment difference at Week 28 is no longer statistically significant. The implementation procedure for the tipping point analysis is described in Appendix 17.5. The combinations of delta adjustments that tip the result from statistically significant to insignificant, along with the corresponding insignificant p-values, will be presented in a table and may be presented in a figure.

A complete-case sensitivity analysis will also be performed to test the robustness of the multiple imputation procedure. The ANCOVA analysis for the first key secondary endpoint will be repeated using only subjects with observed data at Week 28. Subjects who are missing any component of the Week 28 second key secondary endpoint will be excluded from the analysis.

Descriptive statistics and LS means for the complete-case sensitivity analyses will be presented by treatment group along with the LS-mean treatment difference, 95% confidence intervals, and nominal p-values.

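### The tipping-point analysis of the Week 28 glucocorticoid endpoint shifts imputed doses but never imputed androstenedione, so children with a known dose decrease and a missing A4 are not stressed

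*SAP*

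**What the plan says.** **Scoring.** Under SAP 9.4.2 a child with a dose decrease and uncontrolled Week 28 A4 is scored 0%. A child with a dose increase keeps the observed change whatever the A4.

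**Imputation.** SAP 17.2 states its scope as "For subjects with incomplete or missing data at Week 28 (ie, missing glucocorticoid dose, androstenedione, or both", so A4 may be imputed on its own. SAP 9.4.2 joins the two components with the word and, but SAP 9.5.1 and Protocol 13.6.1.3 agree with 17.2, and I read the plan that way. Where A4 is missing, control "will be determined based on the imputed Week 28 androstenedione value", and the change becomes 0% if that value shows no control. On-drug children are imputed from same-arm Week 28 completers. Off-drug crinecerfont children are imputed from retrieved dropouts or, if these are too few, from placebo.

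**A known dose without A4 is foreseen.** SAP 6.7 reads the dose from the medication eCRF. "If a subject has a Week 28 visit performed based on the analysis visit window but androstenedione was not collected at this visit", the safety-lab date is used to read it, and failing that the vital-signs date.

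**The stress test.** SAP 9.4.2.1 gives the aim: "A tipping point sensitivity analysis will be performed to assess the robustness of the missingness assumptions". It names the quantity to be shifted as the "imputed Week 28 serum glucocorticoid daily dose values". Step 1 of SAP 17.5 adds delta only for children "originally missing the Week 28 glucocorticoid daily dose value". The other branch, "If Week 28 glucocorticoid daily dose is non-missing: percent change from baseline", uses the observed dose. Step 2 then sets the change to 0 under the condition "If the subject does not have androstenedione control at Week 28". The deltas move in steps of 1 on the dose scale, upward for crinecerfont and downward for placebo.

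**The concern.** A tipping-point analysis should ask how unfavourable the unseen data must be before the conclusion changes. Here the unseen data are of two kinds, and only one is made worse. For a child with an observed dose decrease and no A4, the imputed A4 decides between full credit and 0%. Most such children would be on drug, and their A4 is drawn from completers in their own arm. That is the assumption a tipping point should challenge, and 17.5 leaves it untouched.

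The other planned analyses do not fill the gap. The complete-case run in 9.4.2.1 drops these children. In 9.4.2.2, the run without zeroing ignores A4, the 150% and 180% runs relax the control rule, and the latest-dose and highest-dose runs impute Week 28 in the same way. None makes an imputed Week 28 A4 less favourable. The SAP already has the tool: 17.3 adds delta to imputed A4 for the primary endpoint, though only at Week 4.

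At stake is what may be concluded about the robustness of the last endpoint in the fixed testing sequence, not its estimate or its type I error.

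**Working it through.** **1. The plan's own figure.** The only sizing figure is the power for the primary endpoint (SAP 3.3). With 54:27 and two-sided 0.05, d = 286.2/345.02 = 0.83 gives 93.6% by the noncentral t, and d = 0.70 gives 83.5%. Both agree with the stated values of above 90% and above 80%. Only the 54:27 allocation carries over to this endpoint.

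**2. Score as delta changes.**

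| Week 28 data | Dose used in 17.5 | A4 used in step 2 | Does the score respond to delta? |
|---|---|---|---|
| Dose missing, A4 known | imputed + delta | observed | yes, if controlled |
| Both missing | imputed + delta | imputed, unshifted | yes, in imputations that show control |
| Dose known, A4 missing | observed | imputed, unshifted | no |

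In the last row nothing depends on delta. If every missing case falls there, each imputed dataset is identical at every delta, and so is the pooled p-value.

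**3. Simulation of 17.2 and 17.5.** Settings: 54:27, 100 imputations, ANCOVA with pooling, 60 trials per scenario, and k crinecerfont children with missing data. The effects and the SD of 18 are assumed.
- A4 alone missing (k = 2, 4, 6): dose deltas of 1, 5, 10 and 50 changed p by exactly 0.0 in every trial.
- Both missing, k = 6, true difference 15: 73% of significant trials tipped by delta 10 and 100% by delta 50. The procedure works where it applies.
- A4 alone missing, k = 6, true difference 15, with imputed A4 raised until every such child was uncontrolled: median p rose from 0.0013 to 0.0042, and 9% of significant trials tipped.

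**4. Size of the omitted shift.** Let m crinecerfont children have a known decrease and a missing A4, with mean cut r and imputed-control share c. Scoring them all 0% moves the crinecerfont mean by m × r × c / 54. All three inputs are assumptions: m = 2 to 5, r = 20 to 30%, c = 0.65 to 0.80. Per child, r × c runs from 20 × 0.65 = 13 to 30 × 0.80 = 24.
- m = 2: 26/54 to 48/54 = 0.5 to 0.9 points
- m = 3: 39/54 to 72/54 = 0.7 to 1.3 points
- m = 5: 65/54 to 120/54 = 1.2 to 2.2 points

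SE of the difference = SD × √(1/54 + 1/27) = SD/4.243, which is 4.7 for SD 20 and 7.1 for SD 30 (assumed). The ratio runs from 0.48/7.07 = 0.07 to 2.22/4.71 = 0.47 standard errors. This counts the crinecerfont side only.

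**5. When could it change a conclusion?** With c = 0.80, the SE held fixed and 76 df:

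| Observed difference, SD | Starting p | Children, mean cut | Shift | p after |
|---|---|---|---|---|
| −10, 18 | 0.021 | 3, 30% | 1.33 | 0.045 |
| −10, 18 | 0.021 | 4, 30% | 1.78 | 0.056 |
| −10, 18 | 0.021 | 6, 20% | 1.78 | 0.056 |
| −12, 20 | 0.013 | 6, 30% | 2.67 | 0.051 |
| −15, 20 | 0.0021 | 8, 30% | 3.56 | 0.018 |

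A difference of −20 with SD 20 also survives 8 such children.

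**The case against.** The strongest reply is that the group is small and the harm bounded. Several of its points stand.

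- The plan narrows A4-only missingness. SAP 6.3.5 substitutes the post-dose A4 when the pre-dose value is absent, and children of at least 6 years and 20 kg have a 3-hour sample. The Week 28 window runs from Day 169 to the first open-label dose and takes in unscheduled and repeat visits. The fallback cannot help when hormone labs were missed altogether, or in younger or lighter children with no 3-hour sample.
- Only children with a dose decrease matter, and the worst a crinecerfont child can score under the control rule is 0%.
- Off-drug crinecerfont children are already imputed cautiously.
- SAP 7.1 tabulates on-drug children with a missing endpoint by arm, and the complete-case run shows whether the result leans on imputed values. Neither separates missing A4 from missing dose, and neither stresses A4.

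A reader might infer that A4-only missingness is the commonest pattern because dose comes from a medication log, and hence that the analysis will look robust whatever the truth. The documents do not support this. They give no rates by component. The dose is read at the date of a Week 28 assessment and needs Week 28 height and weight, so a child who has withdrawn would usually lack both components and is stressed by 17.5. A p-value constant in delta requires every missing case to be A4-only. SAP 6.7 shows that the pattern is possible, not that it dominates.

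**Conclusion.** The gap is real and follows from the text alone: one of the two imputed components is never made less favourable, and children with a known dose decrease and an imputed A4 keep their score at every delta. The consequence is conditional and modest. On the assumed inputs the untested worst case is 0.07 to 0.47 standard errors. It could overturn a result starting near p = 0.01 to 0.02 with four to six such children, and would not overturn the stronger results examined. No figure for missingness, effect or SD of this endpoint is in the documents, so the size is illustrative; the mechanism is not. The change is worth making because, without it, a statement that no delta tips the result cannot be interpreted unless the number of A4-only cases is known.

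**What to change.** 1. Add one bounding run to SAP 17.5. Score every crinecerfont child with a dose decrease and an imputed Week 28 A4 as uncontrolled (0%), and every such placebo child as controlled. Run it alone and combined with the dose deltas. Only if significance is lost is a graded A4 delta needed to locate the tipping point.
2. Reconcile step 2 of 17.5 with 9.4.2 so that only decreases are set to 0 when A4 is uncontrolled. As written, step 2 zeroes every uncontrolled child, including one whose dose has been pushed above baseline by a positive delta. Raising A4 alongside dose would then erase unfavourable increases on crinecerfont. The parallel sentence in 17.2 needs the same qualifier. This step should come before any A4 delta.
3. Apply the minimum of 0 from 17.2 to delta-adjusted doses, since the placebo delta falls without a stated floor.
4. Report by arm how many children are missing dose only, A4 only, or both.

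The cost is SAP wording and a little extra programming, with no new data. The downside is a possibly less favourable sensitivity result.
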